SOCIAL, BEHAVIORAL, and NON-CLINICAL RESEARCH PLAN

CPHS template v. 04172017

Please complete: **PI: [name]**

Important Note: The CPHS Department (Chair & Scientific) Review Form is required with this application. Find the form in the RAPPORT Library or on the CPHS Website.

- Respond to each item, even if to indicate N/A or not applicable
- Attach and/or upload this form as your 'Investigator Protocol' in Rapport
- If you are completing this form on a Mac, indicate your answer to any checkboxes by bolding or highlighting, or by deleting any incorrect options.

1. Introduction and Background

Cigarette smoking accounts for nearly 1 in 5 preventable deaths in the United States, and approximately 16 million American live with a smoking-related disease. Fortunately, smoking cessation is associated with health improvements, including reduced cardiovascular disease, lower cancer risk, and improved life expectancy. Reducing cigarette smoking has been advocated for those not yet ready to quit, and cigarette reduction has been shown to longitudinally predict eventual cessation. Evidence suggests that smoking is highly sensitive to environmental stimuli (e.g., triggers).

One potential approach to reduce smoking is implementation intentions (II), which has shown promise in reducing cigarette use. These II interventions help individuals identify critical situations where smoking is likely to occur and then develop appropriate alternative responses to avoid cigarette use. When II is delivered as a brief, single session intervention, II increases cessation rates relative to control conditions.

Although II is well-suited for EMI because the brief messages are designed to be contextually relevant, to our knowledge, no research has evaluated whether repeated administration of II delivered by EMI reduces cigarette use, though EMIs featuring remotely and repeatedly delivered II messages increase physical activity and decrease alcohol consumption. EMI-II may be beneficial with greater exposure and when delivered in the contexts where a behavior, such as smoking, is likely to occur. This study aims to test an ecological momentary intervention of implementation intentions (EMI-II) to reduce cigarette smoking. This evaluation will combine EMI-II with daily ecological momentary assessments (EMAs), which are brief surveys in which participants report their current context and recent behavior and events.

2. Objectives and Hypotheses

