The first page of the baseline features a consent form (electronic through Qualtrics via an “agree” answer choice) and be offered an electronic copy to download. Consenting participants will complete baseline questionnaires, including demographics and psychological/behavioral assessments (as described in the assessments described below). We expect the baseline assessments to take approximately 30 minutes of participants’ time. During the baseline, participants will be randomized to either an intervention/follow-up condition or a waitlist-control/intervention condition. Each condition (intervention, wait-list, follow-up) will last for approximately 14 days, and participation in each condition will last for approximately four weeks after completing the baseline assessment.

During the approximately four-week study period, participants will be asked to complete an online survey each week. This will be the only study activity during the wait-list condition and the follow-up condition.

During the 14-day intervention period (the details of which are below), participants will complete mini-surveys presented using ecological momentary assessment (EMA; questions/questionnaires asked at a given time point outside of a laboratory setting via a mobile device). EMAs will be sent to participants via text message (i.e., short message service [SMS]) scheduled using the Chorus platform (see Chorus information document). The EMAs will assess conditions surrounding smoking and smoking behavior (see EMA Questions for content). We will ask participants to respond to EMAs for 14 consecutive days. We will prompt them five times daily to inquire about smoking risk behavior and recent nicotine use. Prompts will be sent during the participant's waking hours. A randomly selected 40% of EMAs will include one of the participant's Implementation Intention messages as the final item, permitting repeated delivery of the intervention content in real time.

Study participants will be compensated at the end of their study period via Amazon gift card or MasterCard gift card.

The following supplemental materials will be uploaded to the Rapport website:

- Consent form
- Screening questionnaire
- Baseline assessment
- Weekly survey questions
- EMA questions
- Sample study ads
- Procedural checklist
- Sample emails
- Confirmation phone call script
- Participant compensation visual
- Chorus information

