We expect materials such as the study ads, procedural checklist, participant compensation visual, confirmation phone call script, and emails to evolve over time based on participant feedback. Contact information and links within these documents will be updated once they are finalized.

4. Analysis

Describe any qualitative tests and measures as well as quantitative methods:

Aim 1

Hypothesis 1: At least 75% of participants who start the EMA + EMI-II component will complete the two-week active study period. To determine feasibility, the number of participants who complete the two-week EMI-II period will be divided by the number of participants who start the EMI-II period.

Hypothesis 2: Participants will rate the acceptability of the EMI-II at least a 3.5 out of 5 on average. Acceptability will be calculated by determining the mean score on the AIM.

Aim 2

Hypothesis 1: Participants receiving EMA + EMI-II will show greater reductions in self-reported smoking than participants assigned to a wait-list control. Test by comparing rates of smoking with generalized linear mixed-effects models within the negative binomial family, this accounts for the interdependence of observations within subjects and accounts for the count data of the outcome. Here the rate of change in the number of combustible cigarettes reported in the timeline follow-backs will be

examined by testing an interaction between time and condition. A significant interaction would suggest a differential change in the number of combustible cigarettes smoked across the intervention conditions. The intervention will be tested by including the baseline assessment, as well the change across weeks 1 and 2 of the study (comparing active EMI-II for the intervention group and no-intervention for the wait-list control). **Hypothesis 2: Self-reported cigarette smoking during the next EMA following II presentation will be lower relative to cigarette smoking reported in EMAs that do not proximally follow II delivery.** Test by constructing multilevel dynamic structural equation models nesting the response from the microintervention compared to the no-intervention periods. Robust maximum likelihood estimation will be utilized to account for the ordinal nature of the data.

5. Study Progress Monitoring

Note: appropriate monitoring may include periodic assessment of the following:

- data quality
- timelines
- recruitment and enrollment

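### The Aim 2 Hypothesis 2 model specifies no adjustment for answers given before the randomised message in the same EMA, which may cost power and requires a stronger missing-data assumption

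*Combined protocol and SAP*

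**What the plan says.** Section 4 describes the Hypothesis 2 analysis in two sentences. The model is: "Test by constructing multilevel dynamic structural equation models nesting the response from the microintervention compared to the no-intervention periods". The estimation is: "Robust maximum likelihood estimation will be utilized to account for the ordinal nature of the data". The hypothesis itself is that "Self-reported cigarette smoking during the next EMA following II presentation will be lower relative to cigarette smoking reported in EMAs" that do not closely follow a message. No covariate, lag term or missing-data assumption is named.

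Sections 1 and 3 show what each EMA holds. Section 1 calls EMAs "brief surveys in which participants report their current context and recent behavior and events". Section 3 says: "The EMAs will assess conditions surrounding smoking and smoking behavior", and adds that the five daily prompts ask about risk behaviour and recent nicotine use. On the message it says: "A randomly selected 40% of EMAs will include one of the participant's Implementation Intention messages as the final item".

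Section 4 gives the pre-message answers no role in this test. Section 6c mentions contextual factors only for a later line of research on what interacts with the intervention.

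**The concern.** Because the message comes last, the other answers in that EMA cannot have been changed by it. They are baseline values for that one randomisation, and they exist equally for message and no-message EMAs. Section 1 itself says that smoking responds strongly to triggers in the environment, so it is reasonable to expect context and risk answers to predict the next report.

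Two things are at stake.

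- **Power.** A momentary effect is likely to be small against large moment-to-moment variation. Unused predictors of that variation cost power.
- **Missing outcomes.** The outcome is seen only if the next prompt is answered, and answering happens after the message. Some non-response is foreseen: Section 12 sets a bonus at 32 of 35 prompts per week, and Section 5 provides for reminders and withdrawal. Without the pre-message answers, the analysis must assume that answering is unrelated to smoking given only message status and any lagged smoking. With them, that is assumed only within levels of context and risk, which is easier to believe.

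**Working it through.** **The plan's own figure.** Section 9b states power above 90% for Hypothesis 2 without an effect size, alpha, sidedness or response rate, so it cannot be reproduced. As a reference I used the usual test of a constant proximal effect, an F test with df (1, N−2) and noncentrality N × T × A × p(1−p) × d² / (1−R²). From the documents: N = 65 (upper limit, Section 9a), T = 5 × 14 = 70 and p = 0.40. Two-sided alpha of 0.05 is assumed. A is the share of usable prompts.

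| A | d needed for 90% power | Power at d = 0.10 |
|---|---|---|
| 100% | 0.100 | 90.2% |
| 90% | 0.105 | 87.0% |
| 70% | 0.119 | 77.7% |
| 50% | 0.141 | 63.3% |

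The stated power is therefore neither confirmed nor refuted.

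**Gain from adjustment, linear scale.** The last prompt has no successor, so T = 70 − 1 = 69. With 80% of prompts answered independently (assumed), both the message EMA and the next one are answered in A = 0.8 × 0.8 = 0.64 of cases. With d = 0.10 (assumed), the noncentrality is 65 × 69 × 0.64 × 0.24 × 0.01 = 6.89, divided by (1−R²). R² is the residual variance explained beyond any lagged smoking; its range is assumed. The critical F(1, 63) is 3.99.

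| R² | Noncentrality | Power |
|---|---|---|
| 0 | 6.89 | 73% |
| 1% | 6.96 | 74% |
| 10% | 7.65 | 78% |
| 20% | 8.61 | 82% |
| 30% | 9.84 | 87% |

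**Ordinal scale.** The factor √(1−R²) for the standard error belongs to a linear outcome. In a check with a binary logit as stand-in (n = 3,000, covariate explaining about 10/20/30% of latent variance), adjustment raised the coefficient's standard error by about 4/8/14%. Power still rose, from about 72 to 74%, 59 to 67% and 54 to 58%. The power gain is real, but the linear figures do not carry over.

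**Missing next reports.** A linear within-person simulation used 65 people, 70 prompts, a true effect of −0.10 and 400 replicates. The covariate slope was 0.5 (strong) or 0.2 (weak), residual SD 0.8, and the autoregression of outcome and covariate 0.3 each. Mean estimates with the strong covariate:

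| Answering depends on | No covariate | Lagged outcome only | Pre-message covariate |
|---|---|---|---|
| Nothing (70% answer at random) | −0.101 | −0.102 | −0.101 |
| Context | −0.099 | −0.101 | −0.100 |
| Context plus message | −0.134 | −0.130 | −0.100 |
| Context × message | −0.218 | −0.208 | −0.099 |

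With the weak covariate, the last two rows are −0.114 and −0.145 unadjusted, and −0.100 and −0.097 adjusted.

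**What adjustment cannot repair.** Suppose there is no true effect, but a message cuts answering from 80% to 75% only in intervals with smoking. If a share s of intervals includes smoking, the observed odds ratio is [0.75s / (0.80(1−s))] / [s/(1−s)] = 0.75/0.80 = 0.94, whatever s is. The same ratio appears within every covariate stratum, so adjustment leaves it unchanged.

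**Precision of a response check.** Starting from 65 × 69 × 0.8 = 3,588 answered EMAs, the contrast in next-prompt response has SE √[0.16 × (1/(0.4 × 3,588) + 1/(0.6 × 3,588))] = 0.0136, about 1.4 percentage points, treating prompts as independent.

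**The case against.** The strongest reply is that the plan is silent rather than wrong. A dynamic model ordinarily carries the lagged outcome, and recent smoking is one of the same-EMA answers, so part of the adjustment may already be intended. A reader might infer that the plan excludes or ignores these answers; the documents do not say so. This part of the reply stands, and it is why R² above counts only what the items add beyond lagged smoking. It does not dispose of the point: in the simulation the lagged outcome alone left most of the missing-data bias.

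A second reply is that each message is randomised, so the unadjusted test is sound. That stands for complete data, for answers missing at random regardless of context or message, and, in the linear simulation, when answering depends on context alone. A reader might infer that the planned contrast is invalid; it is not.

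A third reply is that the items' predictive value is unknown. The EMA item list is a separate document, and no R² is given. This also stands. A reader might infer that every message contrast is noisier than it need be, but at R² of 1% the gain is less than half a point of power. Nor may one read the linear reduction in standard error into the ordinal model, or expect adjustment to cure selection on smoking itself.

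**Conclusion.** The point holds as a gap in power and robustness, not as a flaw that invalidates the test. The Hypothesis 2 plan specifies no adjustment for answers that are already collected and that precede the randomised message, and it states no missing-data assumption. On a linear scale, with d = 0.10 and 80% response assumed, the power given up ranges from under 1 point (R² 1%) to about 14 points (R² 30%). On the ordinal scale there is also a gain in power, of a size the documents do not allow one to fix. The missing-data argument is the stronger one: if answering depends on both message and context, the unadjusted estimate can be off by a third or more of the true effect with a strong covariate (−0.134 or −0.218 against −0.10), and less with a weak one. In these scenarios the error exaggerated benefit; its direction depends on the mechanism. All effect sizes, response rates, R² values and simulation settings are assumptions.

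**What to change.** In Section 4, for Hypothesis 2:

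1. Regress smoking at the next scheduled EMA on the randomised message indicator plus a short prespecified list of pre-message answers from the EMA at which the message was or was not given: recent smoking, smoking risk and context. Use the same items for message and no-message EMAs, and say whether lagged smoking is already in the model.
2. Treat an unanswered next prompt as missing in that model, and state the assumption made about it.
3. Report the randomised contrast in next-prompt response after a message versus no message (SE about 1.4 points at 80% response). This is the check on selective answering, including selection on smoking itself, which covariates cannot remove.

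The cost is SAP wording and a few model terms, with no new data. The downside is small: on an ordinal scale the message effect becomes conditional on the covariates and should be reported as such. The list should be fixed before outcome data are seen, since with the present wording a later choice of covariates would be open to question.
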